2.8 CLINICAL PROCEDURES AND SCHEDULE OF EVALUATIONS

This section describes the clinical procedures for evaluating study participants and follow-up after administration of study drug.

Study visits, including screening, will occur at the UMB Institute of Human Virology clinic or one of the clinics mentioned in the study roster based upon scheduling availability to accommodate each treatment group. Participants in the pharmacokinetic or viral kinetic substudy will be seen at the University of Maryland Medical Center.

UMB Study Team Roles at Washington, DC community clinics: Members of the study team have been actively involved in patient care at the community clinics (Unity's Parkside and Walker-Jones). Unity will sign a UMB Reliance Agreement prior to initiating any study activities. The site AI and collaborating investigator may see subjects at non-study visits and will communicate findings to UMB study team. The UMB research coordinators will also oversee research operations in the clinics and at the UMB IHV clinic. The UMB study staff will see participants for all scheduled and unscheduled visits and study withdrawal.

If subjects are seen in the Community: All phlebotomy will be done by a phlebotomist working in the clinic or clinic staff. A specimen bag and specimen tubes will be prepared by UMB staff and will be labeled with the participant's first three initials of last and first name and study number. All laboratory studies will be performed by UMB and will be reviewed by UMB staff on a weekly basis. Copies of results will be sent to the primary care provider and scanned into the electronic medical record at the participating clinic.

Clinic staff will not participate in study-related visits unsupervised by UMB study staff. Participants will be given a calendar of scheduled study visits and will be informed that any clinic visits outside of scheduled study visits may be either unscheduled visits or non-study visits. All visits related to the treatment of HCV will be considered study related. Any other medical problems will be addressed by the participant's primary provider. Participants will receive this information when given the visit calendar.

The primary responsibility of the site AI and the community clinics is to provide timely and effective communication regarding any potential adverse events if a subject/patient is seen for care outside of the normal study visit.

2.8.1 Screening

Each patient will provide informed consent of his/her free will prior to commencement of any study procedures according to ICH and Code of Federal Regulations (CFR). Each patient will be provided a copy of the signed informed consent form.

After a patient has provided informed consent, the Investigator and other study personnel will determine if the patient is eligible for participation in the study. Screening may begin up to 8 weeks prior to dosing to allow for a possible liver biopsy if one has not been performed within 36 months prior to the first dose of study drug (Day 0) and is indicated for disease staging as specified in the inclusion criteria. An optional research liver biopsy will be offered to subjects during screening (and at end of treatment) with the aim of having paired research samples on up to 20 subjects on the study.

Screening will include a review of the inclusion/exclusion criteria and completion of all screening procedures as outlined in the Schedule of Tests, Section 5.1. Screening tests within the last 8 weeks prior to screening visit that have been done as part of routine medical care or at an outside facility (with the exception of chemistries, hCG, HIV, CBC with differential, coagulation studies) can be used if within the acceptable time frame. Known HIV infected participants will not have an HIV test, but will have HIV RNA and CD4 T-Cell count testing.

The standard consent includes permission for HIV testing (in those not previously known to be infected), optional liver biopsy, and storage of blood and tissue samples. HLA testing may be tested for this study if not on file, because this information will be useful for the evaluation of HCV-specific immune responses.

Screening procedures do not need to be repeated within the 8 week screening window unless clinically indicated. Once the screening window has elapsed, patients may be rescreened at the discretion of the PI.

2.9 RANDOMIZATION AND BLINDING

This is an open-label, phase IIB clinical trial, and will be without blinding. Randomization will not be employed, as all participants will be allocated to 12 weeks of the same therapy.

2.10 HISTORY AND PHYSICAL

All subjects will have a History and Physical during the screening process as part of final determination of protocol eligibility. Physical exams will be performed with study point visits at Day 0, Week 4, Week 12 and Post-treatment Weeks 12 and 24. Directed physical exam will be done as needed at other study points. On arrival at the clinic for study visits, subjects will have their vital signs obtained and females of childbearing potential will undergo a pregnancy test (if appropriate per visit day, see Schedule of Tests, Section 5.1), clinical laboratories drawn, and a review of the study restrictions. Subjects will be asked about their state of health and use of any concomitant medication since the previous study visit. They will also be questioned about AEs, their adherence with study restrictions, and their adherence to study drug administration. A complete list of study procedures and lab tests to be performed is in the Schedule of Tests, Section 5.1.

In addition, subjects may be seen at unscheduled visits for a grade 3 or 4 AE or any unexpected AE (adverse event) or potential toxicity.

Some of the visits have flexibility regarding when they need to occur. The window period for visit schedules is as follows:

- Days 0, 3(PK/VK participants only), no window
- Optional Week 1 (+/- 3 days)
- Weeks 2, 4 (+/- 3 days)
- Weeks 8 and 12 (+/- 7 days)
 - Optional End of therapy Liver Biopsy (+/-14 days)
- Post Therapy Weeks 4, 12, 24 (+/- 10 days)

2.11 STARTING SOF/VEL/VOX (DAY 0)

The participant will be started on SOF/VEL/VOX on Day 0. Blood will be drawn for HCV viral loads, immunologic studies, and for storage prior to dosing. A pregnancy test will be done for females with childbearing potential and the pregnancy test must be negative prior to dosing with study drugs. The subject will undergo a history and physical exam on Day 0, prior to starting study medications.

2.12 OPTIONAL PK/VK SUBSTUDY

Participants who are eligible and interested in participating in the optional PK/VK substudy will undergo timed blood draws at baseline, 1, 2, 4, 8, 24, and 72 hours after initiating study medication.

2.13 WEEK 1 VISIT

Participants will either have a telephone phone follow up visit to assess for adverse events and adherence or they will come to the clinic for an in person study visit that will include clinical and research blood draw.

2.14 WEEK 2 VISIT

In addition to scheduled study events, the second bottle of study medication will be dispensed.

2.15 WEEK 4 VISIT

During this visit, HCV RNA will be obtained to determine if virologic-response based treatment stopping criteria have been met. Subjects who fail to achieve >2 log₁₀ HCV RNA drop at this time (unless >2 log drop would be below LLOQ) will be discontinued from therapy unless a review by the PI/LAI/Medical Monitor (MM) determines otherwise, and the last bottle of study medication will be dispensed.

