2.20.2 Criteria for Premature Withdrawal and Stopping Rules

Subjects have the right to withdraw from the study at any time for any reason. Subjects who withdraw early or who are terminated from study by the Investigator will not be replaced unless they have received no study drugs. In addition to the criteria for stopping subject treatment described in Dose Modification and Treatment Failure Sections, the Investigator or designee also has the right to withdraw subjects from the study for any of the following:

- 1. Development of life-threatening infection (requiring withdrawal of study drugs for more than 6 weeks) or malignancy.
- 2. Participant's desire to leave study.
- 3. Pregnancy or breastfeeding.
- 4. Participant's non-compliance. If a subject misses 5 or more total study visits or > 3 weeks of study drug, the subject will be removed from the protocol at the discretion of the Investigator or designee.
- 5. Termination of study.
- 6. Development of liver decompensation with elevated Child-Turcotte-Pugh score of 8 or more.
- 7. If SOF/VEL/VOX FDC is permanently discontinued by the pharmaceutical company.
- 8. Development of a medical condition, such as hepatocellular carcinoma, that in the opinion of the Investigator, it is in the subject's best interest to discontinue study drug even if criteria requiring drug discontinuation have not been met.
- 9. Request of the primary care provider or Investigator if s/he thinks the study is no longer in the best interest of the subject.
- 10. Clinical reasons believed life threatening by the physician.
- 11. If the subject is judged by the Investigator to be at significant risk.
- 12. Subjects may decide at any point not to have their samples stored. This will be treated as a withdrawal of the consent and in this case, the Principal Investigator will assure the destruction of all known remaining samples and report what was done to both the subject and to the IRB. This decision will affect the subject's participation in this protocol but may not affect participations in any other protocols at UMD.

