3.4.1 Dose Modification for SOF/VEL/VOX

Dose modifications will not be permitted. If a subject forgets to take the medication at the correct time, it may be taken later in the day; however, no more than a single dose should be taken on any calendar day. The subject should resume the standing dosing schedule on the next day. Any treatment interruption or discontinuation will be recorded including the reason for the interruption or discontinuation.

3.4.2 Treatment Failure / Drug Discontinuation

See also Criteria for premature withdrawal of subjects (2.20.2). Subjects will be considered treatment failures and will discontinue SOF/VEL/VOX FDC if they meet any of the following criteria while taking study drugs:

- HCV RNA greater than LLOQ after 2 prior consecutive HCV RNA values less than the LLOQ
- Greater than a 1 log₁₀ increase in HCV RNA from nadir
- Less than a 2 log₁₀ decline in HCV RNA after 4 weeks of treatment (unless >2 log drop would be below LLOQ)
- HCV RNA \geq LLOQ after 8 weeks of treatment

If any of these should occur in a patient who is currently on study drugs, the subject should return within one week for a confirmatory test. If the confirmatory test also meets the same criteria, the subject will be considered a treatment failure and should be discontinued from therapy. The anticipated clinical impact of discontinuation should be discussed in advance with the Medical Monitor (MM) if possible, particularly if discontinuation is thought to pose a risk to the overall clinical wellbeing of the subject. Those who are discontinued will continue to follow the general study schedule of assessments unless unwilling to do so, in which case they may be seen at least every 12 weeks for safety and research labs until the end of the study. Subjects will be followed closely for resolution of active laboratory abnormalities or adverse events which are considered related to the study agents prior to starting the revised schedule.

Subjects who meet any of the following laboratory criteria must stop all study medication(s):

- Elevation of ALT >5x OR AST >5x Day 0, confirmed by immediate repeat testing
- Abnormal elevation of ALT >3 x Day 0 *and* total bilirubin >2 x ULN, confirmed by immediate repeat testing
- Elevation of ALT >15 x ULN confirmed by immediate repeat testing
- Any Grade 3 or greater rash associated with constitutional symptoms
- Any Grade 4 event assessed as related to treatment with SOF/VEL/VOX FDC
- Pregnancy

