3.4.4 Viral Co-infection Rebound Schema

For HIV suppressed subjects taking ARVs, at least two consecutive and uptrending postbaseline visit plasma HIV RNA levels \geq 400 copies/mL (at least two weeks apart) will be considered HIV virologic rebound.

Following an initial HIV RNA result of \geq 400 copies/mL, subjects will continue to take their current ARV regimen and be asked to return to the clinic after 2 weeks for a scheduled or unscheduled blood draw for confirmation of HIV virologic rebound. If HIV virologic rebound is confirmed at the scheduled or unscheduled visit, the blood samples from this visit will be used for HIV genotype/phenotype testing. If no resistance to the subject's current ARV regimen is detected, the subject may continue on current ARV regimen.

HCV study drug should be continued unless safety events or HCV response based stopping criteria warrant the discontinuation of the study drug, as outlined in Section 3.4 of the protocol.

For those with chronic HBV infection taking chronic suppressive therapy, if HBV flare does occur, monitoring and treatment plan will be discussed with medical monitor on an individual basis.

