8.5 SPECIFIC STUDY HALTING CRITERIA

8.5.1 Criteria to Pause Enrollment

- **Study will be paused** and the MM will be asked to review the data if 1: 3 participants experience virologic or therapeutic treatment failure while receiving treatment (see Dose Modification 3.4.1 and Treatment Failure Sections3.4.2)
- Dosing will be discontinued if 3 or more participants develop a similar related Grade 4 toxicity (excluding neutropenia, anemia, anorexia, weight loss and ALT and AST elevations). Further dosing will require review and approval after discussion with the MM. Grade 4 toxicities that result from patient non-compliance with medications for unrelated events will not be considered toward discontinuation.
- Enrollment will also be halted if the PI decides to stop or cancel the study or if the IRB or the FDA requests that the study be stopped.

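### Sections 2.15 and 3.4.2 give different stopping rules for the same week 4 HCV RNA result: they differ on confirmation, on override and on the cut-off

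*Combined protocol and SAP*

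**What the plan says.** Section 2.15 (Week 4 Visit) has HCV RNA drawn to see whether "virologic-response based treatment stopping criteria have been met". A subject who does not reach a drop of more than 2 log10 (with an exception where such a drop would fall below LLOQ) "will be discontinued from therapy unless a review by the PI/LAI/Medical Monitor (MM) determines otherwise".

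Section 3.4.2 (Treatment Failure / Drug Discontinuation) lists a decline of less than 2 log10 after 4 weeks, with the same LLOQ exception, among its failure criteria. Its lead-in says that subjects who meet a criterion *will* discontinue. It then adds a step: "the subject should return within one week for a confirmatory test". After that: "If the confirmatory test also meets the same criteria, the subject will be considered a treatment failure and should be discontinued from therapy". On the Medical Monitor it says: "The anticipated clinical impact of discontinuation should be discussed in advance with the Medical Monitor (MM) if possible", above all where stopping might itself harm the subject.

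Other sections treat 3.4 as the home of the rule. Section 2.20.2 refers to "criteria for stopping subject treatment described in Dose Modification and Treatment Failure Sections". Section 3.4.4 keeps HCV drug going during HIV rebound unless safety events or "HCV response based stopping criteria warrant the discontinuation of the study drug, as outlined in Section 3.4 of the protocol". Section 8.5.1 pauses the study for Medical Monitor review if "3 participants experience virologic or therapeutic treatment failure while receiving treatment", and cites 3.4.1 and 3.4.2. None of these withdraws or repeats the exception in 2.15.

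**The concern.** This is a subject-level stopping rule, and the protocol states it twice with different content. Under 2.15 alone, one assay value is enough to stop drug. Under 3.4.2 the same value only triggers a repeat. A spurious or borderline week 4 result could therefore cost a subject most of a course that might have cured the infection.

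In the other direction, 2.15 gives a named review the power to continue, while 3.4.2 gives the Medical Monitor a consultation and no stated power to override. Continuing a true non-responder matters because section 6.1.4 names multiclass resistance as a risk of unsuccessful treatment. What is at stake is subject protection and consistent conduct, not the primary analysis.

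**Working it through.** **The two rules side by side**

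| Element | Section 2.15 | Section 3.4.2 |
|---|---|---|
| Result that triggers action | drop of 2 log10 or less | drop below 2 log10 |
| LLOQ exception | yes | yes, the same |
| Repeat test | not mentioned | within one week |
| Action | stop by default | lead-in: *will* stop; after confirmation: *should* stop |
| Override | PI/LAI/MM review | none stated; MM discussion if possible |

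1. *Confirmation.* Section 2.15 says the sample is drawn to see whether the stopping criteria are met, and 2.20.2 and 3.4.4 place those criteria in section 3.4. A careful reader can therefore import the repeat test. Section 2.15 itself does not say so, and read literally it acts on one value.
2. *Override.* This cannot be imported either way. Section 2.15 states it and 3.4.2 does not. Section 3.4.2 uses both *will* and *should* for the stop, so it does not settle the matter alone.
3. *Cut-off.* The rules part only at a decline of exactly 2 log10: 2.15 catches it and 3.4.2 does not. In practice that depends on rounding.

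**Size**

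Inputs: 12 weeks of once-daily dosing (3.3), 28 tablets per bottle (3.2.2), HCV RNA at weeks 4 and 8 (5.1), planned N = 120 (4.1).

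- Full course: 12 × 7 = 84 doses = 3 bottles × 28.
- Wrong stop at the week 4 visit: 84 − 28 = 56 doses lost, 56/84 = 66.7%. This is the maximum; it falls if dosing continues while the result is awaited.
- Wrong continuation: the next scheduled check is week 8, where HCV RNA at or above LLOQ is a 3.4.2 criterion. Extra doses: 8 × 7 − 4 × 7 = 28, plus up to 7 for confirmation, so 28 to 35 of 84 (33.3% to 41.7%) on the nominal schedule, before result turnaround. The visit windows in 2.10 (±3 days at week 4, ±7 at week 8) move the 28 to between 18 and 38.
- SVR12: one subject is at most 1/120 = 0.83 percentage points.
- Number of subjects: the documents give none. If the 95–97% efficacy in 1.6.4 carried over, 3% to 5% of 120, or 3.6 to 6 subjects, would fail for any reason, and true week 4 non-responders would be some part of these. No rate is given for erroneous values.

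**The plan's own figure.** The point does not depend on the stated power, but it reproduces. The exact two-sided test of 70% with N = 120 and equal tails rejects at 73 or fewer, or 95 or more, responders. Power is 0.968 at 85% and 0.641 at 80%, as in Table 4-1. Neither stopping rule enters that calculation.

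**The case against.** The best reply is that the two sections can be read together: repeat test, discussion with the Medical Monitor, stop by default, exception by review. The wording of 3.4.2 supports this. Confirmed virologic failures *should* be discontinued, whereas subjects who meet the safety criteria *must* stop, so the virologic rule leaves some room. A discussion held before stopping, about whether stopping is harmful, fits the review in 2.15. This narrows the conflict. It does not close it, because the lead-in to 3.4.2 says *will* discontinue, neither section refers to the other on this point, and 2.15 can still be followed without a repeat test.

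Three stronger readings are tempting, and the documents do not support them.

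- A reader might infer that a confirmed failure kept on drug escapes the three-failure pause in 8.5.1. It does not. Section 8.5.1 points to 3.4.2, where the confirmed result alone makes the subject a treatment failure; stopping drug is a separate and softer instruction. The exception in 2.15 concerns discontinuation only. Doubt remains only for a subject handled under 2.15 without a repeat test, or with a drop of exactly 2 log10.
- A reader might infer that different clinicians would go different ways with identical results. Section 4 describes a single-center trial, 2.15 gives the exception to a PI/LAI/MM review, and under 2.8 the university's own study staff see participants at all scheduled and unscheduled visits.
- A reader might take the 56 remaining doses as the extra exposure of a non-responder who is continued. That ignores week 8. Section 2.16 states no review exception, and a rise of more than 1 log10 from nadir is also a criterion.

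**Conclusion.** The point holds as an inconsistency between two statements of one stopping rule. They differ on whether a repeat test comes first, on whether a review may override, and on the result at exactly 2 log10. The first difference could end treatment on a single unconfirmed value. The second leaves open whether a confirmed week 4 non-responder may stay on drug.

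Severity is low. Few subjects are likely to be affected, though that rests on the background efficacy and not on any stated count. Further exposure after a wrong continuation is limited to about 28 doses plus up to a week for confirmation, provided the week 8 criterion is applied as written. The SVR12 definition, sample size and power are unchanged. The 8.5.1 count already includes confirmed failures, so no defect in the pause rule is claimed.

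**What to change.** In 2.15, replace the stopping sentence with a reference to 3.4.2: decline of less than 2 log10 at week 4, the same LLOQ exception, and a confirmatory test within one week before any discontinuation. Say openly in the amendment that this changes 2.15 for a drop of exactly 2 log10, which would no longer trigger a stop.

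In 3.4.2, add that a PI/LAI/MM decision to continue may be made only after the confirmatory result, and must be documented with its reason. This keeps the clinical discretion that 2.15 intends.

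A sentence in 8.5.1 saying that confirmed failures count whatever the treatment decision is optional clarification.

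The cost is one sentence in 2.15 and one in 3.4.2. No visit or test is added, because the repeat test is already in 3.4.2, and no drug is added, because the last bottle is already dispensed at week 4.

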2.16 WEEK 8 VISIT

During this visit, HCV RNA will be obtained to determine if virologic-response based treatment stopping criteria have been met.

2.17 WEEK 12 / END OF TREATMENT VISIT

Week 12 will mark the last dose of SOF/VEL/VOX FDC to be administered. In addition, if a patient's participation terminates prior to Week 12, the Week 12 assessments may be performed at any end-of-treatment visit.

2.18 FOLLOW-UP VISITS AFTER STUDY DRUG DISCONTINUATION

After discontinuation of the study drug, subjects will be followed at Weeks 4, 12, and 24 after completion of therapy. All subjects will be assessed for sustained virologic response (SVR₁₂) at the post-treatment week 12 visit, to occur at study week 24. A serum pregnancy test will be done

with each visit up to 30 days after stopping study drug, in women of childbearing potential, as appropriate.

2.19 FAILURES, EARLY TERMINATION AND EARLY TREATMENT DISCONTINUATION

Participants who prematurely discontinue study agents due to toxicity will be followed closely for resolution of symptoms, until final outcome is known or until the end of the study follow-up period.

Participants requiring discontinuation, as well as those who elect to discontinue study drugs prior to treatment completion for medical or personal reasons, will continue to follow the general study schedule of assessments unless unwilling to do so, in which case they may be seen at least every 12 weeks for safety and research labs until the end of the study. The participant should have an end of treatment visit scheduled as soon as possible after all therapy is discontinued if willing. Any subject continuing in the study will be followed closely for resolution of active laboratory abnormalities or adverse events that are considered related to the study agents. Participants with undetectable HCV RNA at the end of treatment should continue to follow the scheduled SVR4, SVR12, and SVR24 visits following the date of their last dose of therapy while remaining undetectable.

Participants who have detectable HCV RNA at the end of treatment or who relapse posttreatment will be asked to return for additional visits at least every 12 weeks after the end of treatment for up to a total of 24 weeks or on a separate natural history protocol to determine the persistence of any HCV populations with treatment-emergent substitutions conferring resistance to SOF or GS-5885 or VOX. Any subject continuing in the study will be followed closely for resolution of active laboratory abnormalities or adverse events that are considered related to the study agents.

Samples collected will be used to determine the durability of response or the dynamics of any changes in resistance conferring mutations. The reason for any early termination should be documented.

